#### 14.4.3. Analyses of Secondary and Other Endpoints

Similarly, the secondary analyses will estimate the proportion of participants with severe (Grade 3 or higher per [CoFAR Grading Scale for Systemic Adverse Reactions Version 3.0](#)) systemic allergic reactions within 90 minutes, Grade 2 or higher (per [CoFAR Grading Scale for Systemic Adverse Reactions Version 3.0](#)) within 48 hours, and anaphylactic reactions (Levels 1-3) per [Brighton Collaboration Criteria](#) within 90 minutes to either dose of the Pfizer-BioNTech COVID-19 Vaccine and independently to the Moderna COVID-19 Vaccine between the HA/MCD and comparison populations. Again, these estimates will be presented with their 95% exact confidence intervals. Due to the likelihood of these events to be extremely rare, no inferential analyses are planned.

An estimate of the proportion of participants with systemic allergic reactions to the first dose of the Pfizer-BioNTech COVID-19 Vaccine and independently the Moderna COVID-19 Vaccine in the HA/MCD population will be conducted. These estimates will be presented together with their 95% exact confidence intervals. Likewise, the estimate of the proportion and 95% exact confidence interval will be reported for the second dose conditional on no systemic allergic reaction to the first dose to each vaccine.

Another secondary analysis will be conducted to estimate the placebo-adjusted proportion of participants experiencing systemic allergic reactions to the first dose of either the Pfizer-BioNTech COVID-19 Vaccine and independently the Moderna COVID-19 Vaccine in the HA/MCD population. The placebo-adjusted proportions will be estimated as the differences in proportions between the first active vaccine dose versus the corresponding placebo vaccine arm. These estimates will be reported together with their corresponding 95% exact unconditional confidence intervals. Exact p-values will be calculated using an unconditional test. Details for implementation of the secondary analyses will be included in the statistical analysis plan.

Additionally, we will estimate the proportions of participants with systemic allergic reactions to the second vaccine dose (no placebo arm), first vaccine dose within the placebo arm, and their difference for the Pfizer-BioNTech COVID-19 Vaccine and independently the Moderna COVID-19 Vaccine in the HA/MCD population. These estimates will be presented together with their 95% exact confidence intervals.

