7.2.2. Primary Analysis of the Primary Endpoint

If systemic allergic reactions are observed, we will compare the proportions of participants experiencing a systemic allergic reaction to the Pfizer-BioNTech COVID-19 Vaccine and independently to the Moderna COVID-19 Vaccine between the HA/MCD and comparison populations. The point estimate of the difference in proportions between populations within each vaccine is estimated as p_1-p_0 with $p_1=x_1/n_1$ and $p_0=x_0/n_0$ and will be reported, together with the corresponding 95% exact unconditional confidence interval. The proportion difference will be tested using a Barnard's Exact Unconditional Test with a two-sided test using the central method of doubling the one-sided p-value. No multiplicity adjustment will be applied to these two primary endpoints.

```
*** Primary Analysis (Barnard's);
ods output BarnardsTest=BarnardsTestOutput;
proc freq data = d_1 order = data;
  title "Primary";
  where dose = 'E' and protocol<5;
  tables group*resp / riskdiff;
  exact riskdiff barnard;
* High computational power, only run on an as needed basis;
run;
```

The p-value is equal to (BARNARDSTESTOUTPUT.NVALUE1)*2 where BARNARDSTESTOUTPUT.NAME1='XPL_RDIF1'.

```

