7.3. Secondary Endpoints

All secondary endpoints will be analyzed for participants enrolled under version 1.0 through 4.0. If sufficient numbers of children are enrolled, then adults 18 years of age and older will be also be analyzed separately from children.

7.3.1. Secondary Endpoint 1

Endpoint: The proportion of participants who experience a severe (Grade 3 or higher per [CoFAR Grading Scale for Systemic Allergic Reactions Version 3.0](#)) systemic allergic reactions within the 90-minute post-vaccination observation period to either dose of each vaccine.

Computation: A Grade 3 or higher systemic allergic reaction, categorized as yes or no, is defined as a participant having a Grade 3 or higher (per CoFAR Grading Scale V3.0) systemic allergic reaction to either active dose 1 or active dose 2 (categorized as yes) or to neither active dose (categorized as no).

Participants who do not have a systemic allergic reaction to the 1st active dose but missing data for their 2nd active dose will be removed from this analysis (complete case analysis).

Analysis: This analysis will be carried out as outlined in Section 7.2.2. A sensitivity analysis will be carried out as outlined in Section 7.2.3.

7.3.2. Secondary Endpoint 2

Endpoint: The proportion of participants who experience an anaphylactic reaction (Levels 1-3) per Brighton Collaboration Criteria within the 90-minute post-vaccination observation period to either dose of each vaccine.

Computation: An anaphylactic reaction (Levels 1-3) per Brighton Collaboration Criteria, categorized as yes or no, is defined as a participant having an anaphylactic reaction (Levels 1-3) per Brighton Collaboration Criteria to either active dose 1 or active dose 2 (categorized as yes) or to neither active dose (categorized as no).

Participants who do not have a systemic allergic reaction to the 1st active dose but missing data for their 2nd active dose will be removed from this analysis (complete case analysis).

Analysis: This analysis will be carried out as outlined in Section 7.2.2. A sensitivity analysis will be carried out as outlined in Section 7.2.3.

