    ((dose = 'D1' & Placebo = 'Yes') | (dose = 'D2' & Placebo = 'No'));
  class dose;
  model resp(event = '1') = dose / dist=binomial link = logit;
  lsmeans dose / e ilink diff exp;
  store out=genmod;
  ods output coef = coeffs;
run;
%NLMeans(instore=genmod, coef=coeffs, link=logit, title= Priming Prop
Diff);
```

Handling of Missing Data

Participants with missing data for their 2nd active dose for reasons other than systemic allergic reactions in their 1st active dose will be removed from this analysis (complete case analysis).

Participants with missing data for their 2nd active dose because of a systemic allergic reaction to their 1st active dose (inherent missingness given the current design) will be examined using an extreme case scenario (replacement of all 2nd active dose missing by either yes or no). If the result from this extreme case scenario differs and if there is at least 10 systemic allergic reactions in the 1st active dose a tipping point analysis will be conducted.

Notes

The same analysis will be repeated for the Moderna COVID-19 Vaccine.

7.3.4. Secondary Endpoint 5

Objective (First dose comparison to Placebo)

Assess the proportion of participants with systemic allergic reactions to the Pfizer-BioNTech COVID-19 Vaccine in the HA/MCD after adjusting for placebo

Endpoint

The proportion of participants who experience a systemic allergic reaction (CoFAR Grade 2 and above regardless of tryptase, or CoFAR Grade 1 with elevated tryptase [1.2 x baseline plus 2 ng/ml]) within the 90-minute post-vaccination observation period to the first dose of the Pfizer-BioNTech COVID-19 Vaccine after adjusting for placebo administration

Model Specification

- Endpoint is as defined above.
- Endpoint will be analyzed using Barnard's unconditional exact test.

Model Checking & Diagnostics

This analysis will not be carried out if there are no systemic allergic reactions for the placebo dose.

Model Results Presentation

Proportion difference, 95% exact unconditional confidence interval and p-value will be presented for the comparison between 1st dose (active arm) and placebo dose (placebo arm)

Placebo + Pfizer-BioNTech/Placebo + Moderna COVID-19 Vaccine (**placebo**) vs Pfizer-BioNTech COVID-19 Vaccine (**1st**)

Placebo + Pfizer/Placebo + Moderna	placebo	1st	2 nd
Pfizer	1 st	2 nd	

SAS Code

```
*** 1st dose comparison to Placebo;
proc freq data = d_1;
  title "1st dose comparison to Placebo";
  where group = 'HA/MCD' &

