    ((dose = 'P1' & Placebo = 'Yes') |
    (dose = 'D1' & Placebo = 'No' ));
  tables dose*resp / riskdiff;
  exact riskdiff barnard;
run;
```

Supportive Statistical Analyses

If there is an issue with the calculation of the Barnard's Exact Unconditional Test, we will perform a univariate logistic regression. NLMeans macro will be used to obtain the proportion difference and 95% confidence interval. There will be no adjustment for covariates

```
*** 1st dose comparison to Placebo (Sensitivity);
proc genmod data = d_1;
  title "1st dose comparison to Placebo (Sensitivity)";
  where group = 'HA/MCD' &
    ((dose = 'P1' & Placebo = 'Yes') |
    (dose = 'D1' & Placebo = 'No' ));
  class id dose;
  model resp(event = '1') = dose / dist=binomial link = logit;
  lsmeans dose / e ilink diff exp;
  store out=genmod;
  ods output coef = coeffs;
run;
%NLMeans(instore=genmod, coef=coeffs, link=logit, title= 1st dose
comparison to Placebo Prop Diff);
```

Handling of Missing Data

Participants with missing data for their placebo or 1st active dose will be removed from this analysis (complete case analysis).

Notes

The same analysis will be repeated for the Moderna COVID-19 Vaccine.

7.3.5. Secondary Endpoint 6

Endpoint: The proportion of participants who experience a systemic allergic reaction (CoFAR Grade 2 and above) within 48 hours of either dose of each vaccine.

Computation: A Grade 2 or higher systemic allergic reaction, categorized as yes or no, is defined as a participant having a Grade 2 or higher (per CoFAR Grading Scale V3.0) systemic allergic reaction within 48 hours to either active dose 1 or active dose 2 (categorized as yes) or to either active dose within 48 hours (categorized as no). Due to the nature of patient reported events, any systemic allergic reaction reported within 2 days after the date of injection will be counted as occurring within 48 hours.

Participants who do not have a systemic allergic reaction to the 1st active dose but missing data for their 2nd active dose will be removed from this analysis (complete case analysis).

Analysis: This analysis will be carried out as outlined in Section 7.2.2. A sensitivity analysis will be carried out as outlined in Section 7.2.3.

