11. CHANGES TO THE ANALYSES PLANNED IN THE PROTOCOL

As treated sample definition was updated to reflect placebo analyses.

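### Protocol 14.4.3 and SAP 7.3.4 name different placebo comparators for the first-dose contrast, the change is not declared, and the printed code does not carry out the SAP text.

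*SAP*

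**What the plan says.** Protocol 14.4.3 defines the estimate: "The placebo-adjusted proportions will be estimated as the differences in proportions between the first active vaccine dose versus the corresponding placebo vaccine arm". Each vaccine therefore has its own saline control.

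SAP 7.3.4, under Model Results Presentation, takes the Pfizer first dose and compares it with "Placebo + Pfizer-BioNTech/Placebo + Moderna COVID-19 Vaccine". The combined label appears in the comparison line and again in the diagram below it. The diagrams for the paired and priming analyses in SAP 7.3.3 show only the Pfizer placebo arm, so the pooling in 7.3.4 looks deliberate.

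The SAS code in 7.3.4 selects HA/MCD rows meeting "dose = 'P1' & Placebo = 'Yes" (placebo injections) or "dose = 'D1' & Placebo = 'No" (first active doses in the arms without placebo). It has no condition on vaccine or protocol version. A note says to repeat the analysis for Moderna.

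On versions, SAP 7.3 states: "All secondary endpoints will be analyzed for participants enrolled under version 1.0 through 4.0". The primary code in SAP 7.2.2 carries that restriction in its own filter, "where dose = 'E' and protocol<5". The 7.3.3 and 7.3.4 blocks do not.

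SAP 11 lists one change from the protocol: "As treated sample definition was updated to reflect placebo analyses".

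**The concern.** This is the planned contrast of first vaccine dose with saline, the one meant to separate reactions caused by the vaccine from reactions to being injected. It comes with an interval and a p-value. If protocol and SAP name different control groups, the denominator, precision and p-value depend on which document the programmer follows, and that choice could be made after the counts are known.

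The code does not settle the matter, because nothing in it keeps both placebo arms while dropping the other vaccine's first doses. The comparator also affects whether the analysis is done at all: SAP 7.3.4 cancels it when the placebo dose produced no reactions, and a control group half the size is more likely to have none.

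**Working it through.** **Arm sizes.** Protocol 3.1 gives up to 2040 HA/MCD participants, randomised 2:2:1:1 under versions 1.0-4.0. Each arm without placebo: 2040 × 2/6 = 680. Each placebo arm: 2040 × 1/6 = 340. Per vaccine, 680 + 340 = 1020, which agrees with Protocol 14.7. These are planned maxima, not actual enrolment.

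**The plan's own figures.** The documents give no power or expected count for endpoint 5, so the method was checked on the primary comparison (1020 v 680, rates 0.01 v 0.0001, level 0.05). The doubled Barnard test rejects at 7, 11 or 14 HA/MCD reactions when the comparison group has 0, 1 or 2. Exact power is 0.854, meeting the stated minimum of 80%. The exact interval for 0/1020 has upper limit 0.0036, and 10/1020 gives (0.0047, 0.0180), both as in Protocol 14.7.

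**Test.** Tables are ordered by z = (p1 − p0) / √[p̄(1 − p̄)(1/n1 + 1/n0)], with p̄ = (x1 + x0)/(n1 + n0). The one-sided p is the largest tail probability over the common rate, then doubled as SAP 7.2.2 specifies. SAP 7.3.4 names Barnard's test without restating the doubling; its use here is an assumption.

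**What the code returns, by content of `d_1`.**
- One vaccine's arms only: that vaccine's first dose v its own placebo arm, 680 v 340. This is the protocol comparison.
- Both vaccines: all first doses v all placebo doses, 1360 v 680.
- One vaccine's first-dose rows plus all placebo rows: 680 v 680, the SAP text. The SAP describes no such dataset.

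**Main example (assumed counts).** Pfizer first dose 10/680, Moderna first dose 4/680, one reaction in each placebo arm.
- Corresponding arm, 10/680 v 1/340: difference 0.01471 − 0.00294 = 0.0118; z = 0.01176/0.00686 = 1.71; p = 0.14.
- Pooled arms, 10/680 v 2/680: difference 0.0118; z = 0.01176/0.00507 = 2.32; p = 0.022.
- Code on both vaccines, 14/1360 v 2/680: difference 0.01029 − 0.00294 = 0.0074; z = 0.00735/0.00414 = 1.77; p = 0.09.

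Restricting the common rate to below 0.05 gives 0.082, 0.022 and 0.072. Fisher's exact test gives 0.112, 0.038 and 0.108.

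**Other assumed counts.**

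| Pfizer dose 1 | Placebo + Pfizer | Placebo + Moderna | p, corresponding arm | p, pooled arms |
|---|---|---|---|---|
| 8/680 | 1/340 | 1/340 | 0.18 | 0.060 |
| 8/680 | 1/340 | 0/340 | 0.18 | 0.020 |
| 10/680 | 0/340 | 1/340 | 0.032 | 0.0066 |
| 9/340 | 1/170 | 1/170 | 0.14 | 0.038 |

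The second row crosses 0.05 partly because the placebo counts are uneven: pooling halves the placebo rate from 1/340 to 1/680. The first and third rows do not cross.

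**Chance that the analysis is cancelled.** With true placebo reaction rate π (assumed), the chance of no placebo reaction is (1 − π)^n.
- π = 0.001: 0.999^340 = 0.71 for one arm; 0.999^680 = 0.51 for both.
- π = 0.005: 0.995^340 = 0.18; 0.995^680 = 0.03.

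**The case against.** The best defence is that the printed code is a template. No block in SAP 7.2.2, 7.3.3 or 7.3.4 filters on vaccine, yet all are described as analyses by vaccine, and the Moderna note implies that the vaccine is selected upstream. That is a natural reading, and it limits what can be claimed. A reader might infer three rival definitions, or identical tables for Pfizer and Moderna. Both follow only if `d_1` holds both vaccines, which the documents do not say. If `d_1` is cut to one vaccine, the code equals the protocol comparison and there are two definitions. Even so, the code then loses the pooled control that the SAP text asks for.

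A reader might also infer that children from versions 5.0-8.0 will enter the analysis. SAP 7.3 excludes them explicitly, so this would need someone to run the snippet against the text. What stands is that the primary code filters version inside the block, so the same `d_1` is evidently not filtered beforehand, and the secondary code printed for it contradicts the SAP's own rule.

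On disclosure, Protocol 14.4.3 leaves implementation details to the SAP. The change declared in SAP 11 also concerns placebo analyses: the revised as-treated sample in SAP 4 includes anyone given placebo, without splitting by assigned vaccine. That is compatible with pooling but does not state it, and a change of control group is more than implementation.

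Finally, this is a secondary endpoint with no stated power or decision rule, and with equal placebo rates the point estimate does not move. Both are true; the interval and p-value still do.

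**Conclusion.** The concern holds as a conflict between protocol and SAP text over the control group, not declared in SAP 11, with code that does not implement the SAP text and omits the required version condition. These points are textual and rest on no assumed figure.

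The size does rest on assumptions. At planned maximum arm sizes the control group is 340 or 680. In the main example the same difference of 0.0118 has p = 0.14 or 0.022 according to the comparator. That the choice will reverse the conclusion cannot be inferred: it does so for some plausible counts and not for others. The effect on whether the analysis runs depends on an unknown placebo reaction rate. The point should be corrected before the analysis is run, but it does not touch the primary comparison of HA/MCD with the comparison population.

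**What to change.** 1. In SAP 7.3.4 name one comparator. Suggested: the pooled saline group from versions 1.0-4.0, with the corresponding-arm contrast as a sensitivity analysis. Both placebo arms were randomised alongside both vaccine arms under those versions, so the pooled group remains a concurrent randomised control.
2. In SAP 11 declare this as a change from Protocol 14.4.3. No protocol amendment is needed if it is declared there.
3. In the 7.3.4 code restrict only the first-dose rows to the vaccine being analysed and leave the placebo rows unrestricted, or define `d_1` so that it does this.
4. Add `protocol<5` to the 7.3.3 and 7.3.4 code.
5. State that the rule cancelling the analysis refers to the chosen comparator.

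The cost is a few lines of SAP text and code. The small downside is that pooling mixes 0.3 mL and 0.5 mL saline injections, since Protocol 6.1.3.2 matches placebo volume to the assigned vaccine; the sensitivity analysis covers this.

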8. SAFETY EVALUATION

8.1. Overview of Safety Analysis Methods

All safety analyses will be carried out using the safety sample defined in Section 4 unless otherwise noted. Missing safety information will not be imputed. These analyses will not be stratified by site.

Listings will be prepared for all safety measurements. All listings will be sorted in order of treatment, cohort assignment (HA/MCD or Comparison), participant identifier (ID), and time of assessment (e.g., visit, time, and/or event). All displays will be presented separately for adult and child populations.

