### 3. Study Design

#### 3.1. Description of Study Design

This is a multi-center, randomized, initially blinded, phase 2 trial to assess SARS-CoV-2 vaccination reactions in two populations: one population including individuals with a history of recent, severe allergic reactions, poorly controlled allergic asthma, or MCDs and one comparison population without severe allergies or mast cell disorders. The study aims at enrolling up to 2040 HA/MCD and 1360 comparison participants across approximately 30 US sites.

Approximately two-thirds of participants enrolled in each of the 2 groups will be female. This is because the vast majority of cases of anaphylaxis to the COVID-19 vaccines have occurred in women. Enrollment of participants who qualify only on the basis of reactions to multiple unrelated drugs will be limited to approximately 300. Enrollment of the MCD group is anticipated to be at least 200 participants, and not more than 300 participants.

Participants enrolled under protocol versions 1.0 – 4.0 were randomized 2:2:1:1 to receive the Pfizer-BioNTech COVID-19 Vaccine, Moderna COVID-19 Vaccine, placebo + Pfizer-BioNTech COVID-19 Vaccine, or placebo + Moderna COVID-19 Vaccine (Figure 1).

Participants enrolled under protocol versions 5.0 – 8.0 will be randomized 2:1 to receive the Pfizer-BioNTech COVID-19 Vaccine or placebo + Pfizer-BioNTech COVID-19 Vaccine. If enrollment is robust and sustained, active vaccine randomization may be changed to Moderna.

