### 3.5. Stratification, Randomization, and Blinding/Masking

#### 3.5.1. Stratification and Randomization

Randomization will be performed using a validated system configured by the Statistical and Clinical Coordinating Center (SACCC) that automates the random assignment of vaccine groups to study ID numbers. The randomization scheme will be generated by one statistician and reviewed and approved by another statistician at the SACCC.

Under protocol versions 1.0 – 4.0, participants were randomized 2:2:1:1 to receive either the Pfizer-BioNTech COVID-19 Vaccine, Moderna COVID-19 Vaccine, placebo + Pfizer-BioNTech COVID-19 Vaccine, or placebo + Moderna COVID-19 Vaccine. Participants randomized to one of the placebo groups received placebo as a first dose and received two doses of their assigned active vaccine at subsequent visits.

Under protocol versions 5.0 – 8.0, participants will be initially randomized 2:1 to receive the Pfizer-BioNTech COVID-19 Vaccine or placebo + Pfizer-BioNTech COVID Vaccine. If enrollment is robust and sustained, the active vaccine may be changed to Moderna, and participants will then be randomized 2:1 to receive Moderna COVID-19 Vaccine or placebo + Moderna COVID-19 Vaccine.

Randomization will be stratified by site, sex, population (HA/MCD or comparison), and mast cell disorder/idiopathic anaphylaxis (yes or no) within the HA/MCD group. Randomization will occur in permuted blocks with varying block sizes randomly distributed. Randomization data will be kept strictly confidential, accessible only to authorized persons, until the time of unblinding. The clinical site's research pharmacy will dispense the study drug as per the randomly assigned treatments.

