#### 3.5.2. Blinding/Masking and Planned Unblinding

An unblinded pharmacist will prepare each vaccine, and an unblinded qualified medical professional will administer the vaccine in such a way that the participant cannot see the syringe. Unblinded staff may also schedule study visits and conduct procedures other than clinical endpoint assessments. Staff performing clinical assessments will not know whether a participant is receiving placebo or vaccine, or which vaccine a participant is receiving at the first visit. During a follow-up call, scheduled 3 days after the first vaccination/placebo dose, participants will be scheduled for their next dose.

Under protocol versions 1.0 - 4.0, participants and the staff were unblinded during the follow-up call 3 days after the second injection when a third appointment (for those who received a placebo injection first) was, or was not (active vaccinations only) scheduled. Due to the different dosing schedules for the Pfizer-BioNTech COVID-19 Vaccine and Moderna COVID-19 Vaccine, it became apparent to both the site staff and study participant which vaccine had been assigned, once their second injection was scheduled.

Under protocol versions 5.0 – 8.0, the participant, their parents/legal guardians, and staff will be aware of whether a participant received placebo at the phone call 3 days after the first injection when the participant is scheduled for the first active vaccine in approximately 7 days after placebo. Participants, their parents/legal guardians, and staff will not be blinded to vaccine assignment as only one active vaccine will be implemented at a given time.

Vaccination reports to the state and local authorities will be completed after a participant is unblinded.

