# R: Primary Analysis (Barnard's) p-value
library(exact2x2)
t <- with(d_1 %>% filter(dose == 'E' and protocol<5),
table(group,resp))
uncondExact2x2(t[1,2],sum(t[1,]),
t[2,2],sum(t[2,]),
alternative = "less",
parmtype = "difference",
method   = "score",
midp     = TRUE,
control  = ucControl(nPgrid=5000),
conf.int = FALSE)
```

Exact unconditional confidence limits for the risk difference are obtained with SAS procedure PROC FREQ and the RISKDIFF option in the EXACT statement. These RISKDIFF options request exact unconditional 95% confidence limits for the risk (proportion) and risk difference for the 2x2 table respectively. PROC FREQ computes the confidence limits by the tail method, which inverts two separate one-sided exact tests of the risk difference, where the tests are based on the score statistic (Chan and Zhang 1999). The size of each one-sided exact test is at most $\alpha/2$, and the confidence coefficient is at least $(1-\alpha/2)$.

If there is an issue with the calculation of the Barnard's Exact Unconditional Test, we will perform the Risk difference estimates, asymptotic 95% confidence intervals, and p-values using SAS procedure PROC FREQ and the RISKDIFF option without an EXACT statement.

```
*** Primary Analysis (Asymptotic);
proc freq data = d_1 order = data;
  title "Primary";
  where dose = 'E' and protocol<5;
  tables group*resp / riskdiff;
run;
```

Additionally, we will compare the proportion of participants experiencing a systemic allergic reaction (as defined in section 7.2.1) between HA/MCD adult (18 years and older at enrollment) and HA/MCD child (less than 18 years of age at enrollment) populations for each vaccine separately. Children who qualified for the study on the basis of uncontrolled allergic asthma will be excluded from this analysis. The point estimate of the difference in proportions between adult and child populations within each vaccine will be estimated along with its corresponding 95% exact unconditional confidence interval. The proportion difference will be tested using a Barnard's Exact Unconditional Test with a two-sided test using the central method of doubling the one-sided p-value. No multiplicity adjustment will be applied.

In the event that there are not enough subjects in a particular population, the reaction rate will be described descriptively.

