8.2. Adverse Events

All AEs will be classified by system organ class (SOC) and preferred term, according to a standardized thesaurus (Medical Dictionary for Regulatory Activities [MedDRA] version 24.0). The severity of non-allergic AEs will be classified using the FDA Guidance for Industry Toxicity Grading Scale for Healthy Adult and Adolescent Volunteers Enrolled in Preventive Vaccine Clinical Trials (September 2007), and the severity of systemic allergic reactions will be graded using CoFAR Grading Scale for Systemic Allergic Reactions Version 3.0. Each AE is entered on the electronic case report form (eCRF) once at the highest severity. As such, no additional data manipulation is needed to identify events.

An overall summary table will be developed to report the number of events and the number and percentage of participants having at least one event in the following categories:

- AEs
- AEs indicated as systemic allergic reactions

- AEs that lead to study treatment discontinuation
- AEs indicated as serious
- AEs with an outcome of death
- AEs that were reported as being related to vaccine/placebo
- AEs reported by severity

In addition, AEs classified by MedDRA SOC and preferred term will be summarized for each treatment group and overall.

Summary tables will present the total number of events as well as the number and percentage of participants experiencing the events. If a participant experiences the same AE on multiple occasions, the event will be counted once for each occurrence when reporting the number of AEs. When reporting the number of participants experiencing the events, a participant will only be counted once if they experience an event within the particular SOC or preferred term.

Percentages will be based on the number of participants in the safety population.

In addition, treatment-emergent AEs classified by MedDRA SOC and preferred term will be summarized for each treatment group, cohort assignment (HA/MCD or Comparison), and overall. The proportion of participants in each study arm experiencing each type of AE will be compared using a Fisher's Exact test. The frequency of treatment-emergent AEs will also be summarized by SOC and preferred term for severity (grade) and relationship to study treatment.

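### In the child safety tables, the Fisher tests of Pfizer against Moderna pool adolescents randomised between the vaccines with later children who were not, because SAP 8.1–8.2 split by age but not by protocol version

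*SAP*

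**What the plan says.** SAP 8.1 sets one stratification rule for safety output: "All displays will be presented separately for adult and child populations". SAP 8.2 then says of treatment-emergent adverse events: "The proportion of participants in each study arm experiencing each type of AE will be compared using a Fisher's Exact test". It gives no significance level, does not list the contrasts, and does not restrict them by protocol version. Section 8 has no definition of child. The only one in the SAP is in 7.2.2, "child (less than 18 years of age at enrollment", which depends on age alone.

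The endpoint sections do refer to version. The SAP 7.2.1 text and the 7.2.2 code limit the main analysis to versions below 5, and 7.3 says "All secondary endpoints will be analyzed for participants enrolled under version 1.0 through 4.0".

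The protocol runs two designs:
- **Versions 1.0–4.0, ages 12 and over.** Protocol 3.1: "Participants enrolled under protocol versions 1.0 – 4.0 were randomized 2:2:1:1 to receive the Pfizer-BioNTech COVID-19 Vaccine, Moderna COVID-19 Vaccine", plus a placebo-first arm for each vaccine.
- **Versions 5.0–8.0, ages 5–17.** Protocol 3.5.1: "participants will be initially randomized 2:1 to receive the Pfizer-BioNTech COVID-19 Vaccine" or placebo followed by Pfizer. A change to Moderna is possible later, but 3.5.2 says "only one active vaccine will be implemented at a given time".

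**The concern.** Following section 8 as written, the child Moderna column holds adolescents from versions 1.0–4.0, plus children from a later period if the switch to Moderna takes place. The child Pfizer column holds the adolescents' randomised Pfizer counterparts and all the versions 5.0–8.0 Pfizer children. Protocol 4.1 says that enrolment before version 5.0 was very largely adult, and Protocol 14.7 sets a goal of 300 children for Pfizer. The Pfizer column would probably be dominated by children with no concurrently randomised Moderna counterpart.

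The two groups differ in ways that can move adverse-event rates without any vaccine effect. A significant Fisher result between Pfizer and Moderna in children would look like a randomised finding from a randomised trial, yet could come entirely from protocol version. Pooling would also dilute the valid comparison that does exist, the one among versions 1.0–4.0 adolescents.

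**Working it through.** **1. Who enters the child tables**

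| | Versions 1.0–4.0 | Versions 5.0–8.0 |
|---|---|---|
| Under-18s eligible (Protocol 4.2) | 12–17 years | 5–17 years |
| Allocation (3.5.1) | 2:2:1:1, both vaccines at once | 2:1 within one vaccine |
| Pfizer dose (6.1.2) | 30 mcg | 30 mcg at 12–17, 10 mcg at 5–11 |
| Vaccine identity (3.1, 3.5.2) | blinded at the first visit | known |
| Scheduled post-baseline CBCs, no-placebo arm (Appendix 3, Tables A and C) | 3 | 1 |

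The CBC count excludes draws triggered by a reaction. Table A schedules one CBC 1 hour after dose 1, one before dose 2 and one 1 hour after dose 2. Table C schedules only the last of these. Protocol 13.3.1.1 makes a rise in laboratory grade from baseline a treatment-emergent adverse event, so more draws give more chances of an event.

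**2. Which contrasts are affected**

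- *Pfizer v placebo+Pfizer:* allocation is 2:1 in versions 1.0–4.0 (the 2 and the 1 of 2:2:1:1) and 2:1 in versions 5.0–8.0. Each period enters both columns in the same ratio, so pooling does not unbalance them.
- *Adults:* enrolled only under versions 1.0–4.0, so there is nothing to pool.
- *Child Pfizer v Moderna:* versions 5.0–8.0 Pfizer children have no concurrent Moderna arm. This contrast is affected.

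**3. The plan's own figure**

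The documents give no operating characteristic for the safety tests. The nearest child figure is the approximate 80% power in Protocol 14.7 (180 v 120; 0.05 v 0.0001). An exact unconditional test with the one-sided p-value doubled reproduces it at 79.6%. It confirms the child sample size but does not bear on this point.

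**4. False-positive rate with no vaccine effect**

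Inputs from the documents: 300 × 2/3 = 200 Pfizer no-placebo children in versions 5.0–8.0, and 3 v 1 scheduled CBCs.

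Assumptions: two-sided alpha 0.05; M = 15, 30 or 60 adolescents in each no-placebo arm of versions 1.0–4.0 (3M = 45, 90 or 180 in all under 2:2:1:1); probability q of a graded change at each CBC; draws independent; no switch to Moderna.

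Event probability is 1 − (1 − q)³ in versions 1.0–4.0 and q in versions 5.0–8.0. For q = 5%, 10% and 20% this gives 14%, 27% and 49% against 5%, 10% and 20%. The pooled test compares M Moderna with M + 200 Pfizer, so the concurrently randomised share of the Pfizer column is 15/215 = 7%, 30/230 = 13% or 60/260 = 23%. Exact enumeration of the Fisher rejection rate gives:

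| q per CBC | Pooled, M = 15 / 30 / 60 | Versions 1.0–4.0 only |
|---|---|---|
| 1% | 6% / 9% / 13% | under 1% |
| 2% | 10% / 15% / 20% | 0.1–1.3% |
| 5% | 22% / 33% / 39% | 1.2–2.6% |
| 10% | 39% / 51% / 63% | 1.8–3.0% |
| 20% | 56% / 78% / 89% | 1.7–3.5% |

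Two of the three Table A draws fall at the same visit. Counting them as one (two effective draws) lowers the range for q = 5–20% to 10–46%.

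**5. The same check without CBCs**

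Taking generic event rates in the two periods and assuming 20, 40 or 80 adolescents per no-placebo arm:

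| Rate, versions 1.0–4.0 v 5.0–8.0 | Pooled |
|---|---|
| 50% v 50% | 3.5–4.2% |
| 50% v 40% | 9–18% |
| 20% v 10% | 23–33% |
| 50% v 30% | 35–61% |

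Restricted to versions 1.0–4.0, the rate is 2.0–3.3% throughout.

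**The case against.** A reader might infer that Pfizer and Moderna children were never randomised against each other. The documents do not support that. Versions 1.0–4.0 admitted ages 12 and over, Figure 1 of the protocol names adolescents, and they were allocated to both vaccines concurrently. If no switch to Moderna occurs, every Moderna child has randomised Pfizer counterparts; the difficulty is that the Pfizer column also contains others. Nor are between-arm safety tests compromised in general, as step 2 of the working shows.

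The stakes can also be overstated. No primary or secondary objective compares the two vaccines in children, and SAP 8.2 attaches no alpha or decision rule to its tests. The child Moderna column may be very small: with 3–5 adolescents per arm and q = 5%, the pooled rejection rate is only 6–14%. Tests are run by type of event, so rates for a single term may be well below a rate for any graded CBC change. Solicited symptoms are collected for 7 days after each injection in every version, so sampling frequency does not inflate them.

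The age split in section 8 also fits the adult–child comparison in SAP 7.2.2 and the separate child analysis foreseen in 7.3.

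All of this stands, and it limits the size and reach of the point. It does not make the pooled test valid. SAP 8.2 does not say whether Fisher's test is pairwise or across all arms, but both readings include Pfizer against Moderna unless it is excluded.

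**Conclusion.** Wrong as written, limited to the child Pfizer–Moderna safety contrast. The SAP's stated rule produces a test that looks randomised but is confounded by age, Pfizer dose, enrolment period, blinding and laboratory sampling. That conclusion is structural and needs no assumed numbers.

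The size does need them. With no vaccine effect and alpha taken as 0.05, the false-positive rate runs from no inflation when event rates are equal in both periods, through about 10–20% at 2% per CBC, to 22–89% at 5–20% per CBC. The same test within versions 1.0–4.0 gives about 0–4%. The upper range rests on independent draws and on 15–60 adolescents per arm. The documents state neither the adolescent numbers nor the event rates, so no single value should be quoted as the expected error.

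**What to change.** In SAP 8.1–8.2:

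- Show child adverse-event tables separately for versions 1.0–4.0 (ages 12–17) and versions 5.0–8.0 (ages 5–17).
- Limit any child Fisher test of Pfizer against Moderna to participants randomised concurrently under versions 1.0–4.0. If the test is meant to span all four arms, run that form only within versions 1.0–4.0.
- Across versions, or across sequential vaccine periods within versions 5.0–8.0, report Pfizer and Moderna children descriptively without a test.
- Tests of Pfizer against placebo+Pfizer, and all adult tests, can stay as they are.

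The cost is a short addition to the SAP wording and one by-variable in the table programs, with no new data. The downside is more and smaller child tables. Applying the same split to the summaries in 8.4 and 8.5 is optional, since those sections are descriptive and contain no tests.
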